### How the consent process will be conducted

Written consent in person, face to face will be obtained for the initial portion of the study.

The study team will reach out via phone to subjects that participated in the initial portion of the study to inform them of the 1 and 2 year follow-up portion of the study and see if they are interested in participating. If a participant expresses interest, the study team will email a copy of the consent addendum to the participant and schedule a remote visit (phone call or MyChart video visit) to reconsent the participant.

The participant will then sign the electronic consent addendum in DocuSign and the study staff will then DocuSign the same consent addendum. A copy of the signed consent addendum will then be emailed to the participant.

### Waiting period

There is no designated waiting period between informing prospective participant and obtaining consent. Prospective participants can take the consent form home to review, and return for the informed consent discussion at a later visit if they are interested in participating.

### Step for the potential participant's understanding

The study investigators and clinical research coordinators will be present to explain the protocol, review and obtain the informed consent, to administer initial tasks, to assist in downloading smartphone applications and provide the device.

Participants will have the opportunity to read the informed consent document (attached) and be given the opportunity to ask any questions or address any concerns.

The study investigators and clinical research coordinators will review the informed consent, and describe to the participant what the study entails, including instructions on how to end their participation in the study at any time / their right to withdraw without any repercussions, and risks, benefits, and alternatives to participating in the study.

Study investigators and clinical research coordinators will assess participant understanding of the study, as well as address any questions or concerns to the participants satisfaction.

Participants will sign the informed consent if they agree to participate and be provided with a copy of the signed document.

### Any process to ensure ongoing consent.

The study team will be soliciting information from participants throughout the study and address any ongoing questions or concerns.

## Follows HRP-090 - SOP - Informed Consent Process for Research.

Yes.

### **Non-English Speaking Participants**

Participants will be included if they are able to speak and read English due to Leva smartphone application availability in only English at this time.

## 9.0 Process to Document Consent in Writing

#### HRP-091 - SOP - Written Documentation of Consent. YES

## 10.0 Setting

Where research procedures will be performed.

- University of Wisconsin's Advanced Pelvic Surgery Clinic
- Participant self-guided treatment at home setting

## **11.0 Study Intervention**

### **Description:**

The Leva Pelvic Health System is a commercially available digital therapeutic system that is FDA-cleared for the treatment of chronic fecal incontinence (symptoms >/= 3 months) in women, for stress, urgency, and mixed urinary incontinence in women, and for pelvic floor muscle strengthening in women. The system includes an intra-vaginal device that pairs with a smartphone application to provide real-time visual feedback about pelvic floor muscle performance during use. The training protocol embedded in the device/app includes 5 cycles of 15-second contraction followed by a 15-second rest period. This 2.5-minute training protocol is completed twice daily. Participants will be instructed to follow this training regimen with the Leva Pelvic Health System for either 8 or 16 weeks. The device will be shut off remotely by Leva at the end of the allocated 8- or 16-week study period and participants will be able to keep or dispose of the device.

In addition to guiding PFMT, the Leva app also provides educational and motivational content in the form of 'daily tasks.' At each training session, participants will have the opportunity to watch a brief educational video or read a short informative message or article presented to them that describes their health condition, helpful behavioral modifications (e.g., toileting posture, breathing exercises, dietary changes), or words of support or motivation. While engagement with these tasks is optional (PFMT can be completed without completing the task), participants will be encouraged to access this content.

### **Drug/Device Handling**

The Research assistant or Principal Investigator (PI) will familiarize the subject with the Leva Pelvic Health System, assist in downloading the app, instruct the subject in the placement, removal and use of the device and the associated smartphone application. This will be completed using a demo device in the clinic.

The Research assistant or PI will complete the designated Leva medical order form and send via secure fax to the commercial entity to notify them of new participant usage. The Leva app requires the study team to prescribe the device to allow the participant to register the device. This is part of the data sharing agreement.

As part of the registration for the device, Axena Health (The Leva Pelvic Health System) will receive a prescription form from study physician and coordinators with information about participant name, date of birth, phone number, email address, and mailing address. This information requested so that the Leva health coaches are able to provide assistance as a part of this program, and in case any replacement devices are needed during the study period in the event of device damage or failure.

The devices will be stored in the study investigator's office in double locked storage. The Research assistant or PI will dispense the device to the participant at the initial study visit.

Each participant will receive additional instructions on device set-up and first use by the designated Leva team, as occurs with typical commercial use.

The device will be shut off at the end of the allocated 8- or 16-week study period and participants will be able to keep or dispose of the devices.

The Leva Pelvic Health System is a commercially available digital therapeutic system that is FDA-cleared for the treatment of chronic fecal incontinence (symptoms >/= 3 months) in women, for stress, urgency, and mixed urinary incontinence in women, and for pelvic floor muscle strengthening in women.

| FDA Regulation | IND Studies | IDE studies | Abbreviated IDE
studies |
|----------------|-------------|-------------|----------------------------|
| 21 CFR 11      | X           | X           |                            |
| 21 CFR 54      | X           | X           |                            |
| 21 CFR 210     | X           |             |                            |
| 21 CFR 211     | X           |             |                            |
| 21 CFR 312     | X           |             |                            |
| 21 CFR 812     |             | X           | X                          |
| 21 CFR 820     |             | X           |                            |

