### Secondary objectives

- To determine the impact of using the Leva Pelvic Health System on the following parameters and to compare these between 8 vs 16 weeks of use:
  - Pelvic Organ Prolapse Quantification System (POP-Q) (physical exam)
  - Brink Scale Score (physical exam)
  - Stool consistency (Bristol Stool Scale)
  - Fecal Incontinence Quality of Life (FIQoL)
  - Sexual Function (PISQ-IR)
  - o Patient Global Impression of Improvement (PGI-I)
  - Patient Satisfaction
  - Estimated Percentage of Improvement
  - Global Pelvic Floor Symptoms (Pelvic Floor Distress Inventory PFDI-20)
- To assess whether 8 weeks of use of the Leva Pelvic Health System is non-inferior to 16 weeks of use for the treatment of fecal incontinence in women assessed by the St.Mark's/Vaizey score at 24 weeks. To evaluate the relationship between adherence to the Leva Pelvic Health System treatment protocol and changes in fecal incontinence symptoms
- To evaluate patient satisfaction and usability of the smartphone application component of the Leva Pelvic Health System (mHealth App Usability Questionnaire MAUQ)
- To characterize parameters of product use, including adherence, coach interaction, and pelvic floor muscle parameters (endurance, lift angle)

- To evaluate self-continuation of pelvic floor muscle exercises, at 16 and 24 weeks.
- To monitor and report on safety and adverse events.
- To evaluate long-term impact 1 year and 2 years from enrollment.
  - St. Mark's/Vaizey Score
  - Stool consistency (Bristol Stool Scale)
  - Fecal Incontinence Quality of Life (FIQoL)
  - Sexual Function (PISQ-IR)
  - Patient Global Impression of Improvement (PGI-I)
  - Patient Satisfaction
  - Estimated Percentage of Improvement
  - Global Pelvic Floor Symptoms (Pelvic Floor Distress Inventory PFDI-20)
- .

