### Data will be collected during the study

- In office examination at first visit and 16 weeks
  - Limited Physical Examination will include the collection of the following data:
    - Vitals (height, weight, pulse, blood pressure)
    - POP-Q
    - Brink Scale Score
- Leva smartphone application surveys administered at 0,4,8,12,16 weeks
  - $\circ$  UDI-6
  - o CRADI-8
- Administration of electronic surveys at 0, 16 weeks and 24 weeks via emailed weblink.
  - o St Mark's (Vaizey)
  - o Bristol Stool Scale
  - o FIQoL
  - PISQ-IR
  - o PGI-I
  - o Patient satisfaction
  - o Estimated percent improvement
  - mHealth App Usability Questionnaire (MAUQ)
  - o PFDI-20
- *Questionnaires, structured interviews, or other assessments.* Attached
- Source records that will be used to collect data about participants. UW Health HealthLink Records (study team will directly access)

Long-term follow-up data

- Administration of surveys at 6 months by mail or email
  - o Bristol Stool Scale
  - St Mark's (Vaizey)
  - o FIQoL
  - o PISQ-IR
  - o PGI-I
  - Patient satisfaction
  - Estimated percent improvement
  - mHealth App Usability Questionnaire (MAUQ)
  - o PFDI-20
- To evaluate self-continuation of pelvic floor muscle exercises, at 16 and 24 weeks.
- Long-term follow up data will be collected by adminstration of electronic surveys completed at 1 year and 2 years from enrollment date:
  - Bristol Stool Scale
  - St Mark's (Vaizey)
  - o FIQoL
  - PISQ-IR
  - o PGI-I
  - Patient satisfaction
  - Estimated percent improvement
  - o PFDI-20

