## 20.0 Study Analysis

### **Statistical Hypotheses**

This is a prospective, pragmatic, non-inferiority randomized control trial.

- Primary alternate hypothesis: 8 weeks of use of the Leva Pelvic Health System is non-inferior to 16 weeks of use for the treatment of fecal incontinence in women assessed by the St.Mark's/Vaizey score at 16 weeks follow up.

-Primary null hypothesis: 8 weeks of use of the Leva Pelvic Health System is not non-inferior to 16 weeks of use for the treatment of fecal incontinence in women assessed by the St.Mark's/Vaizey score at 16 weeks follow up.

-Secondary endpoints:

- To determine the impact of using the Leva Pelvic Health System on the following parameters and to compare these between 8 vs 16 weeks of use at 16 and 24 weeks:

- POP-Q
- Brink Scale Score
- Stool consistency (Bristol Stool Scale)
- Fecal Incontinence Quality of Life (FIQoL)
- Sexual Function (PISQ-IR)

- Patient Global Impression of Improvement (PGI-I)
- Patient Satisfaction
- Perceived Percentage of Improvement
- Global Pelvic Floor Symptoms (Pelvic Floor Distress Inventory PFDI-20)
- To evaluate change (improvement) from baseline to 24 weeks after 8 or 16 weeks of treatment as assessed by St.Mark's/Vaizey score
- To evaluate the relationship between adherence to the Leva Pelvic Health System treatment protocol and changes in fecal incontinence symptoms
- -To evaluate patient satisfaction and usability of the smartphone application component of the Leva Pelvic Health System (mHealth App Usability Questionnaire)
- To characterize parameters of product use, including adherence, coach interaction, and pelvic floor muscle parameters (endurance, lift angle)
- To evaluate self-continuation of pelvic floor muscle exercises, at 16 and 24 weeks.
- To monitor and report on safety and adverse events

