## What data are reviewed, including safety data, untoward events, and efficacy data.

The anticipated risk is minimal; the study team will work together with the Leva team to monitor study progress and identify potential problems, risks, safety concerns, adverse events or reportable events.

The Leva team will send updates regarding safety data and usage data every 4 weeks. If an identified concern or event is unexpected or greater than minimal risk, the study team will be notified by Leva team or participant immediately.

Efficacy data will be reviewed at study completion.

The study team also conduct regular internal reviews of study data and consent forms for compliance.

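### The protocol neither names nor masks the week-16 examiner for POP-Q and Brink, the only examiner-rated efficacy outcomes, and leaves routes by which that person could learn the arm

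*Combined protocol and SAP*

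**What the plan says.** Section 3.0 (Secondary objectives) marks two outcomes as exam-based: "Pelvic Organ Prolapse Quantification System (POP-Q) (physical exam" and "Brink Scale Score (physical exam". Section 20.0 (Statistical Hypotheses) includes both in the list for which the aim is to "compare these between 8 vs 16 weeks of use at 16 and 24 weeks". Section 13.0 sets the timing: "In office examination at first visit and 16 weeks". The schedule of procedures agrees and shows no exam at 24 weeks, so week 16 is the only post-baseline comparison that these two measures can supply.

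On tasks that might touch the allocation, section 11.0 (Drug/Device Handling) says "The Research assistant or PI will complete the designated Leva medical order form and send via secure fax to the commercial entity" and "The Research assistant or PI will dispense the device to the participant at the initial study visit". Section 11.0 (Description) adds: "The device will be shut off remotely by Leva at the end of the allocated 8- or 16-week study period". Section 23.0 says: "The Leva team will send updates regarding safety data and usage data every 4 weeks".

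The design statement (section 13.0) and the randomization statement (section 20.0, permuted blocks, 1:1) say nothing about masking. No section names the role that performs the exam.

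**The concern.** Participants cannot be masked to how long their device works, and the symptom, quality-of-life and satisfaction outcomes are surveys that they complete themselves. For POP-Q and Brink, someone else does the rating, so that person could be kept unaware of the arm at little cost. The plan does not take the opportunity, and it allows the same small team to order and dispense devices, receive usage data and, possibly, examine.

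An examiner who knows that a participant's device went dead eight weeks earlier may expect a loss of function, or may hope to see none. Either expectation can shift a rating, and the direction cannot be predicted. At stake is the week-16 between-arm comparison of these two secondary outcomes.

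**Working it through.** The plan gives no figure on this point, so there is none to reproduce. The check is of the text.

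**1. Which outcomes depend on an examiner?** St. Mark's/Vaizey, Bristol, FIQoL, PISQ-IR, PGI-I, satisfaction, percent improvement, MAUQ and PFDI-20 are electronic surveys (section 13.0). Adherence, endurance and angle are listed as product-use or muscle parameters (section 3.0), and section 16.0 describes cloud capture of device data. These last are neither self-reported nor rated by an examiner. POP-Q and Brink remain. The week-16 adverse event assessment also involves staff judgement, but it is a safety item.

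**2. Could the examiner learn the arm?**

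| Possible route | What the documents say | Does it reveal the arm? |
|---|---|---|
| Order form | Completed by the research assistant or PI; the information listed is identity and contact data (section 11.0) | Not shown. The manufacturer must learn the duration somehow in order to shut the device off, but the documents do not say how |
| Dispensing | Done by the research assistant or PI; nothing says that the device differs by arm | Not shown |
| Usage updates | Sent to the study team every 4 weeks; use must stop at week 8 in one arm because of the remote shut-off | Yes, once weeks 8 to 16 are covered, for anyone who can link the record to the person |
| Linking key | Usage data are coded. Section 16.0 gives key access in one place to the PI, research assistant and coordinators, and in another to the PI and research assistant only | Open if the examiner is one of these; closed for another investigator without key access |
| Participant | Attends the exam knowing the arm; no request not to disclose. Adverse events and self-continued exercise are also assessed at week 16 | Open for any examiner |

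**3. Is the examiner separated from these routes?** No text does so. The PI may handle the order and hold the key, and nothing excludes the PI from examining. Equally, nothing says that the PI does examine.

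**4. Order at the first visit.** Exclusions for fecal impaction on exam and for stage 4 prolapse imply an exam before randomization. The device is dispensed at the same visit, however, and the sequence is not stated.

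**5. Illustration only.** The documents give no size of bias, no SD for Brink or POP-Q, and no named test for them. Assume a two-sided 5% t-test, no true difference, and a systematic rating difference of b SD between arms. With n per arm, the degrees of freedom are 2n − 2 and the noncentrality is b × √(n/2). With 20% attrition, 19 × 0.8 = 15.2, so n is about 15: 28 degrees of freedom and noncentrality b × 2.74. With no attrition, n = 19: 36 degrees of freedom and noncentrality b × 3.08.

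| Assumed b (SD) | False-positive rate, n = 15 | False-positive rate, n = 19 |
|---|---|---|
| 0 | 5% | 5% |
| 0.25 | 10% | 12% |
| 0.5 | 26% | 32% |
| 0.75 | 51% | 61% |

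This shows how such a comparison would respond to a bias. It does not estimate one.

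**The case against.** The strongest reply is that no unmasking is documented. The order form, as described, does not carry the arm, and the device appears to be the same in both groups. Usage data are coded and the key is restricted. Consent is taken by investigators in the plural, so an examining investigator other than the PI might see nothing that identifies the arm. The trial is declared pragmatic, the two outcomes are items in a long secondary list with no stated test or margin, and the primary outcome is an emailed survey that an examiner cannot influence.

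Most of this stands. It limits the point to a missing safeguard on two secondary outcomes. It does not close the gap: coding protects only an examiner outside the group that holds the key, and the plan does not say that the examiner is outside it. Coding also does nothing about disclosure in the exam room. A pragmatic design does not prevent masking a rater.

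A further objection concerns the remedy. The 4-weekly updates combine safety and usage data, and the study team must prescribe the device, so removing one investigator from everything could weaken oversight. This is fair, and the fix has to leave safety reporting as it is.

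**Conclusion.** The point holds as an avoidable weakness in two secondary comparisons. POP-Q and Brink are the only examiner-rated efficacy outcomes, and the plan neither names the examiner nor keeps that person unaware of the arm, while the routes set out above stay open. The size of any bias cannot be derived from the documents, and its direction is unknown.

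A reader might infer three stronger things that the documents do not support:

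- That ordering or dispensing tells the PI the arm and that the PI then examines. Both steps are inference.
- That the primary result is compromised by examiner knowledge. It is self-reported by survey, so it is not exposed to this route, although participants do know their own arm.
- That the trial loses an independent check on its primary result. No section gives Brink or POP-Q that role.

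The conclusion rests on two assumptions: that the usage updates show activity participant by participant, and that the supplied text is the whole plan on masking.

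**What to change.** In section 11.0 (Drug/Device Handling), section 13.0 (Data will be collected during the study) and section 23.0 (What data are reviewed):

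- State that the week-16 POP-Q and Brink are done by an existing investigator who has no access to the allocation, the linking key or the usage part of the 4-weekly updates.
- Assign arm-related tasks and receipt of usage data to the research assistant or a coordinator. Any required prescription should be signed by a study physician who is not the week-16 examiner.
- State that the baseline exam precedes randomization.
- Keep the arm off the exam form, ask participants not to disclose it, and have the examiner record afterwards whether it became known.
- State that safety reports continue to reach the investigators unchanged.

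The cost is a reallocation of tasks, one added field on the exam form and a little more coordination at a single site, with no added visit. Some accidental unmasking will still occur, which is why it should be recorded. The documents do not describe staffing. If existing staff cannot support this separation, the protocol should state that the exams are open and interpret these two comparisons accordingly.

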## 12.0 Study Timelines

Individual participants will be actively engaged in the study for approximately 16 weeks. Longterm follow-up questionnaires will be administered at 6 months (24 weeks from study start). Study enrollment is anticipated to begin in September 2023 and is estimated to be completed within one year.

Participants will be invited to complete follow up surveys for the study at 1 year and 2 years from enrollment.

## **13.0 Procedures Involved**

### Study design

This is a prospective, pragmatic, non-inferiority randomized control trial.

### Schedule of procedures:

| Study Phase      | Screening
/ Enrollment | 16 week
Follow Up
Visit | 24 week
Follow Up | 1 year surveys | 2 year
surveys |
|------------------|---------------------------|-------------------------------|----------------------|----------------|-------------------|
| Visit Number     | 1                         | 2                             |                      |                |                   |
| Informed Consent | Х                         |                               |                      |                |                   |

| Review Eligibility       | Х |   |   |   |   |
|--------------------------|---|---|---|---|---|
| Demographics/Medical Hx  | Х |   |   |   |   |
| Physical Exam            | Х | Х |   |   |   |
| Electronic Study Surveys | Х | Х | Х | Х | Х |
| Vital Signs: BP, HR, RR  | Х |   |   |   |   |
| Pregnancy Test, Urine    | Х |   |   |   |   |
| Prior/Concomitant Meds   | Х |   |   |   |   |
| Clinical Laboratory Eval | Х |   |   |   |   |
| Adverse Event Assessment |   | Х |   |   |   |
|                          |   |   |   |   |   |

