### Minimize risks of harm or discomfort.

The study inclusion and exclusion criteria have been created to allow for a pragmatic trial, but with the intention to prevent harm or discomfort for participants. Specifically, the first exclusion criteria is 'the inability to tolerate insertion of vaginal device (vaginal agenesis, vaginal stenosis, unremitting pelvic pain, within 12 weeks postpartum).'

Participants will be monitored during the study period for any adverse events, risks or safety concerns. Any participant questions or concerns will be communicated with either the study investigators directly or Axena Health, Inc. (The Leva Pelvic Health System) directly and reported to study investigators.

Participants will be provided with surveys to complete at 4 and 6 months from study completion and will have additional opportunity to communicate any adverse events, risks or safety concerns.

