### How the safety information will be collected

The anticipated risk is minimal; the study team will work together with the Leva team to monitor study progress and identify potential problems, risks, safety concerns, adverse events or reportable events. Participants will also be encouraged to call on any identified potential problems, risks, safety concerns, adverse events or reportable events.

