## The frequency of data collection, including when safety data collection starts and ends.

Device usage data and safety data will be collected throughout the study period.

Participants will be instructed to contact study investigators or research coordinators with any questions or concerns at any time during the study.

Complete efficacy data will be collected at study completion and long-term follow up data at 6 months from study start; this data will be compared to baseline data.

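### The only scheduled active adverse event assessment is at week 16, which is 8 weeks after planned last use in one arm and 0 weeks in the other; collection at other times has no defined method

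*Combined protocol and SAP*

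**What the plan says.** **Schedule.** In the Section 13.0 table the row "Adverse Event Assessment" has one mark, under the 16-week visit. The 24-week, 1-year and 2-year columns are empty. Also in Section 13.0, the heading on procedures to monitor participants for safety is answered N/A.

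**Promise.** Section 23.0 (frequency of data collection) states: "Device usage data and safety data will be collected throughout the study period". Section 20.0 (Planned Interim Analysis) says the same.

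**Other channels.**
- Section 23.0: "The Leva team will send updates regarding safety data and usage data every 4 weeks". Events that are unexpected or of more than minimal risk are to be notified at once.
- Section 23.0: "Participants will also be encouraged to call on any identified potential problems, risks, safety concerns, adverse events or reportable events". It adds: "Participants will be instructed to contact study investigators or research coordinators with any questions or concerns at any time during the study".
- Section 22.0 (Minimize risks): "Participants will be provided with surveys to complete at 4 and 6 months from study completion". Through these, participants "will have additional opportunity to communicate any adverse events, risks or safety concerns".
- Section 17.0: the study team reviews medical records at screening, following study visits and at the end of the study.

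**Surveys.** Section 13.0 lists the instruments. In the app, at weeks 0, 4, 8, 12 and 16, they are the UDI-6 and CRADI-8. By emailed link, at weeks 0, 16 and 24, they are the St Mark's, Bristol, FIQoL, PISQ-IR, PGI-I, satisfaction, percent improvement, MAUQ and PFDI-20. No adverse event form is named in either list.

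**End of use.** Section 11.0: "The device will be shut off remotely by Leva at the end of the allocated 8- or 16-week study period".

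**The concern.** Reporting on safety is a stated secondary objective, and in a trial of shorter against longer use, tolerability is one of the grounds on which the shorter course might be preferred. That description is only as good as the way events are elicited.

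The events Section 22.0 expects (vaginal irritation, pain, urinary tract infection) are mostly minor and easily forgotten. The immediate-notice rule is written for unexpected or higher-risk events and would not normally pick these up. If participants are asked about them once, with a different delay since last use in each arm, a lower count in the 8-week arm could partly reflect recall. The text promises continuous collection, but the operational sections do not say who asks what, when, or over what recall period.

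**Working it through.** The plan gives no figure to reproduce here. The check is a count, an interval, and a comparison of sections.

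**1. Scheduled assessments (Section 13.0 table).** Week 16: 1. Week 24: 0. Years 1 and 2: 0.

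**2. Delay from planned last use to the scheduled question** = assessment week − shut-off week (Sections 13.0 and 11.0).
- 8-week arm: 16 − 8 = 8 weeks.
- 16-week arm: 16 − 16 = 0 weeks.

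The question looks back over 16 weeks in both arms. Those weeks comprise 8 on device and 8 off in one arm, and 16 on device in the other. Weeks 16 to 24 have no scheduled assessment in either arm.

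**3. What fills the gaps.**

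| Channel | Section | Timing | Method of eliciting events |
|---|---|---|---|
| Participant calls | 23.0 | Any time | Unsolicited |
| Manufacturer updates | 23.0 | Every 4 weeks | Not stated |
| Record review | 17.0 | Following visits, study end | Finds only events recorded in care |
| App surveys | 13.0 | Weeks 0, 4, 8, 12, 16 | No adverse event form listed |
| Emailed surveys | 13.0, 22.0 | Weeks 0, 16, 24 | Section 22.0 claims an opportunity to report; no form listed |

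None of these is a defined adverse event assessment. The documents do not say whether app surveys and manufacturer updates continue for the 8-week arm between weeks 8 and 16.

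**4. Conflicts between sections.** Sections 20.0 and 23.0 promise continuous collection; Section 13.0 answers N/A for safety procedures and schedules one assessment. Section 22.0 dates the 4- and 6-month surveys from study completion, while Section 12.0 dates the 6-month questionnaire at 24 weeks from study start. If completion meant week 16, then at 4 weeks to the month (the protocol's own 6 months = 24 weeks) the surveys would fall at 16 + 16 = 32 and 16 + 24 = 40 weeks. The schedule has no such contacts.

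**5. How many events to expect.** Section 22.0 quotes 5/182 = 2.75% for irritation and 3/181 = 1.66% for urinary tract infection. Assuming these risks apply per participant, 19 in an arm gives 19 × 0.0275 = 0.52 and 19 × 0.0166 = 0.31 expected events. The chance of seeing at least one, 1 − (1 − p)^19, is 0.41 and 0.27. With counts this small, any comparison between arms can only be descriptive, and one missed event alters it.

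**The case against.** The strongest reply is that the schedule row is not the whole protocol. Section 23.0 provides updates, calls and immediate notice of serious concerns. Section 22.0 provides for evaluation and follow-up of complaints and an added reporting opportunity at the later surveys. Section 17.0 provides record review that does not depend on recall and is the same in both arms; it could reveal a treated urinary tract infection. The device is cleared and described as minimal risk, no between-arm safety test is planned, and the primary endpoint is untouched.

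Much of this stands, and it rules out several stronger readings:
- *That adverse events are collected only once, or not at all at week 24.* This is true of scheduled assessments only.
- *That no survey asks about adverse events.* The questionnaires are attachments that the documents do not include. What can be said is that no adverse event form is listed.
- *That the 8-week arm loses coverage after week 8.* Section 11.0 says the device is shut off; it does not say the app is. The app surveys and updates are described without any exception by arm. The point is unstated, not shown.
- *That ascertainment bias is about twofold.* If 2.75% and 1.66% are taken as 8-week risks (Section 22.0 gives no period), constant risk gives 1 − (1 − 0.0275)² = 5.4% and 1 − (1 − 0.0166)² = 3.3% over 16 weeks. That contrast reflects longer exposure, a real consequence of longer use. It does not measure biased ascertainment.

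The reply does not supply a method. Calls are unsolicited, the updates have no stated way of asking, and record review misses events never brought to care or treated elsewhere.

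**Conclusion.** The point holds as a gap in method and an internal inconsistency. There is one scheduled active assessment, at week 16, placed 8 weeks after planned last use in one arm and 0 weeks in the other, and none is scheduled at week 24. Collection at other times rests on channels that are passive or undefined.

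Unequal recall of minor expected events between arms is possible. Its size cannot be estimated from the documents, and its presence is not demonstrated. The 8 v 0 week interval assumes that use runs to the planned shut-off; earlier stopping would lengthen it in either arm. The consequence is confined to the descriptive safety objective. The change is worth making because it is cheap and because safety counts by duration will be read alongside the non-inferiority result.

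**What to change.** 1. Add one solicited adverse event item, naming the events in Section 22.0 plus an open category, to the study's own emailed surveys at weeks 16 and 24. Use the same wording, mode and recall period in both arms.
2. Send the same short emailed question to both arms at week 8, and optionally at weeks 4 and 12. The existing surveys at those weeks sit in the manufacturer's app, so this is a new email. Sending it identically to everyone avoids depending on the app, and avoids asking one arm by email and the other in the app.
3. Mark these times in the Section 13.0 schedule.
4. Report events by arm per participant and per participant-week of device use, descriptively. The usage data are already collected. At full planned use the denominators would be 19 × 8 = 152 and 19 × 16 = 304 participant-weeks.
5. Reconcile Sections 13.0 (schedule, N/A entry, survey list), 20.0, 22.0 and 23.0. State whether app surveys and manufacturer updates continue for the 8-week arm after shut-off, and align the survey dating in Section 22.0 with Section 12.0.

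Cost: almost nothing for the items at weeks 16 and 24 and for the reporting; one to three short extra emails per participant; and a few more minor reports for the study team to review. No visits are added.
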